We will recruit older Veterans with dysvascular LLA (1-5 years after LLA) to participate in the PABC intervention, which uses established VA Health Care system technology and evidence-based intervention methods. The five key dimensions of feasibility to be assessed are whether Veterans: 1) can successfully participate in the intervention (practicality), 2) tolerate physical activity progression (implementation feasibility), 3) are interested and enjoy the intervention (acceptability), 4) complete the intervention safely (safety), and 5) respond to the intervention with increased activity and decreased disability (responsiveness).^{31,32} Measures of physical activity and disability will be used to establish effect size estimates for the PABC intervention, with the intention of planning a future clinical efficacy trial. Testing will occur at baseline (pre-intervention), three months (end of intervention), and six months, using a two-group randomized crossover design.

Primary Aim: Determine feasibility of using the PABC intervention with older Veterans who have dysvascular LLA by assessing: 1) practicality (measured by retention rate), 2) implementation feasibility (measured by dose goal attainment), 3) participant acceptability (measured by the Intrinsic Motivation Inventory (IMI) – Interest / Enjoyment Subscale), and 4) safety (measured with Adverse and Serious Adverse Events).

Hypothesis 1.1: Retention rate will be at least 85% over the PABC intervention period (i.e., ≤15% attrition).

Hypothesis 1.2: At least 75% of participants will meet the dose goal of a 3% average increase in daily steps per week, across the three months of intervention.

Hypothesis 1.3: Participants will indicate PABC intervention acceptability with a mean score of ≥ 5/7 on the IMI – Interest / Enjoyment Subscale.

Hypothesis 1.4: There will be similar rates of study related (definitely, probably, possibly) adverse events between groups during the first three months (period of direct comparison of intervention versus control).

Secondary Aim: Establish effect size estimates of the PABC intervention (responsiveness)

using physical activity and self-report disability outcomes.

Hypothesis 2.1: The PABC group will have increased activity counts and less self-reported disability than the control group at Month 3, each with effect size estimates ≥ 0.80 (Cohen's d).

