The proposed pilot study is a randomized, tester-blinded design assessing PABC intervention feasibility (Aim 1) and effect size (Aim 2). Randomization ($n=32$) will create two groups (GROUP1 or GROUP2) using computer-generated random blocks of 2 and 4, stratified by amputation level (transtibial and transfemoral). An investigator not involved with testing or intervention ([name]) will conceal group allocation. A crossover design is used to simultaneously accomplish the aims and optimize recruitment (Fig.2). The PABC Intervention will be delivered to both groups (GROUP1 during Months 1-3 and GROUP2 during Months 4-6). The crossover design provides $n=32$ for assessing Aims 1 and 2. Intervention effect retention will be tested at six months for GROUP1 ($n=16$).

D.1. Setting

The study will occur at the VA Geriatric Research Education and Clinical Center (GRECC), where Drs. [name] and [name] have dedicated positions ([name] (GRECC Director)). Intervention delivery will occur with the participant at home and therapist at a VA site with access to tablet interface software (e.g. VA Jewell Motion Analysis Lab or VA Clinical Building South, using VA-supplied and approved mobile-health tablets and wearable activity sensors (FitBit)).

D.2. Participants

Thirty-two participants will be recruited from the Denver VAMC. The target sample is older Veterans diagnosed with PAD and/or DM, who have major LLA. We expect $<15\%$ attrition, with a goal of 26 participants completing.

D.3. Eligibility Criteria

Inclusion criteria: ≥ 50 years of age, LLA 1-5 years prior, Type II DM and/or PAD, and

ambulatory without human assistance, in the home or better using a prosthesis, with assistive device as needed, with assistive device as needed. Exclusion criteria: wheelchair as primary form of locomotion, trauma or cancer-related etiology of the LLA, unstable heart condition, uncontrolled hypertension, acute systemic infection, cancer, recent stroke (within 2 years), or lower extremity wound or ulcer that limits ambulation.

D.4. Recruitment Strategies

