The FitBit sensor will be used to guide the intervention and data from the sensors will NOT include personal health information; with generic accounts will be created for each user without participant-identifiable information. FitBit data will not be used as outcomes, but rather, only to guide the PABC intervention. Outcome data will be managed using the REDCap (Research Electronic Data Capture) platform. REDCap is a secure, web-based application designed to support research data capture, providing user-friendly case report forms, real-time data entry validation (e.g., data type and range checks), audit trails, transaction logs, and a de-identified data export to common statistical packages. The VA Eastern Colorado Health Care System has approved REDCap for research use. More detail is provided in the Human Subjects section.

D.8. Sample Size Estimate

The sample size estimate was based on evidence for activity change in patients with DM and PAD, which indicates a reasonable expected increase of 3% walking activity per week (e.g., steps, distance, time) over 3 months.^{3, 12, 77, 78} A baseline mean (SD) of 2000 (900) steps/day was estimated based on data from our ongoing dysvascular LLA RCT (Section C.3.) and published LLA data.^{49, 79, 80} A 3% weekly increase in steps during intervention, assuming no order effect, would provide an effect size of 0.8 (Cohen's d). Based on those assumptions, a sample size of 13 per group with a crossover design (total n=26) provides >95% power to detect an intervention effect (effect size=0.8, $\alpha=0.05$, two-tailed paired t test). The study is generously powered intentionally, because the assumption of 'no order effect' will not likely hold. We will recruit 32 participants, and expect at least 26 to complete. This 15% attrition estimate is conservative, based on an historical attrition rate <15% in our intervention studies with other older adult populations^{81, 82} and our current dysvascular LLA RCT.

D.9. Data Analysis Plan

Aim 1 (Feasibility of PABC Intervention): The analyses for Aim 1 are based on four hypotheses: H1.1) participant retention, H1.2) dose goal attainment, H1.3) intervention acceptability, and H1.4) safety.

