- H1.1) Retention rate will be assessed using a cut off of 15% attrition (i.e., loss of >6 participants). Mean attrition rate will be compared to the null value of 15% using a one-sample t-test ($\alpha=0.05$). This attrition rate is considered feasible based on previous activity change programs for patients with DM or PAD.^{5, 83}
- H1.2) Dose goal attainment will be assessed by the proportion of participants achieving the goal of 3% average weekly increase in steps, based on activity gains in other intervention studies.^{3, 12, 78} The ability to attain a 3% average weekly step increase for <75% of the participants will be considered a negative result. The proportion of participants attaining a 3% average weekly step increase will be reported (95% CI) and compared to the null value of 75% using a one-sample binomial proportions test ($\alpha=0.05$).
- H1.3) Acceptability of the intervention will be measured with the IMI Interest and Enjoyment subscale, with a mean score of <5/7 considered a negative acceptability result.¹⁰ Mean IMI Interest and Enjoyment score will be compared to the null value of 5.0 using a one-sample t-test ($\alpha=0.05$).
- H1.4) Adverse and serious adverse event (AE/SAE) rates (events/participant) will be compared between groups for Months1-3 (PABC intervention for GROUP1, attention control for GROUP2). We expect similar AE/SAE rates between groups (assessed by Safety Officer and research team).

Aim 2 (Effect Size and Preliminary Efficacy of PABC Intervention): Effect size of the PABC intervention will be calculated with Cohen's d using mean and standard deviation for change in activity counts and LLFDI scores. Statistical inference of group differences for calculation of sample size estimates will be based on linear models with activity counts and LLFDI scores as outcome variables. Explanatory variables in each model will include primary medical diagnosis (PAD, DM, or both), group, and baseline activity count or LLFDI score.

D.10. Expected Outcomes and Interpretation

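### The H1.1 count rule (more than 6 lost) does not implement the 85% PABC-period retention target: it is not 15% of 32, and its denominator and loss window are not stated

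*Combined protocol and SAP*

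**What the plan says.** Hypothesis 1.1 (section A) fixes both the target and the window: "Retention rate will be at least 85% over the PABC intervention period (i.e., ≤15% attrition". Section D.5 places PABC in Months 1-3 for GROUP1 and Months 4-6 for GROUP2. GROUP2 therefore spends three months in attention control before PABC, and GROUP1 has a three-month no-contact wash-out after it.

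The H1.1 entry in section D.9 gives the decision rule: "Retention rate will be assessed using a cut off of 15% attrition (i.e., loss of >6 participants". It adds a test: "Mean attrition rate will be compared to the null value of 15% using a one-sample t-test ($\alpha=0.05". It does not say whether the denominator is all randomised or all who started PABC. It gives no loss window, and it does not say how losses in the control period or the wash-out are treated.

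Three other statements bear on the count. The opening of section D says "The crossover design provides $n=32$ for assessing Aims 1 and 2". Section D.2 says "We expect $<15\%$ attrition, with a goal of 26 participants completing". Section D.8 says "We will recruit 32 participants, and expect at least 26 to complete", and describes this as a 15% attrition estimate.

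**The concern.** Retention is the first of the primary-aim outcomes, and the hypothesis concerns one three-month window that falls at a different calendar time in each group. A GROUP2 participant lost in Months 1-3 never starts PABC. A GROUP1 participant lost in Months 4-6 has already finished it. Neither loss measures the practicality of PABC.

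The rule in D.9 is a bare number of lost participants that matches neither the 15% beside it nor any stated denominator. The same data could be called feasible or not feasible depending on whose losses are counted, and the choice could be made after the losses are known. The result is meant to inform a larger trial.

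**Working it through.** **Inputs.** 32 randomised (section D), with 16 in GROUP1 (section D) and so 16 in GROUP2; 26 expected to complete (D.2, D.8); target of at least 85% over PABC (Hypothesis 1.1); cut-off of more than 6 lost (D.9). The documents give no loss rates by period, so those below are assumptions shown as a range.

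**1. The plan's own count.** 32 - 26 = 6, so more than 6 lost means fewer than 26 completing. As percentages of 32:

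- 15% of 32 = 4.8
- 4/32 = 12.5%
- 5/32 = 15.6%
- 6/32 = 18.75%
- 7/32 = 21.9%

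The 15% limit is passed at five losses, but the count does not trigger until seven. A cut of more than 6 equals a 15% limit only if 6/N is at most 0.15 and 7/N exceeds 0.15, that is for N from 40 to 46. No denominator of 32 or fewer gives it.

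**2. What 85% over PABC allows.** With S starters, the largest permitted number of losses is 0.15 x S rounded down: 4 for S = 27 to 32, and 3 for S = 20 to 26.

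**3. Reading A: only PABC-period losses count.** With all 32 starting, five losses leave 27/32 = 84.4% and six leave 26/32 = 81.3%. Both miss 85% and both pass the count. The chance of this is P(5 or 6 losses) from a binomial with n = 32: 17.6% if the PABC loss rate is 10%, and 34.1% if it is 15%.

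**4. Reading B: every loss among the 32 counts.** Let c be GROUP2 losses before PABC, p losses during PABC, and w GROUP1 wash-out losses. The count fails when c + p + w is 7 or more. The hypothesis is met when (32 - c - p)/(32 - c) is at least 0.85. Both hold, for example, in these patterns:

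| c | p | w | Total lost | PABC retention |
|---|---|---|---|---|
| 4 | 3 | 0 | 7 | 25/28 = 89.3% |
| 3 | 4 | 0 | 7 | 25/29 = 86.2% |
| 0 | 4 | 3 | 7 | 28/32 = 87.5% |

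**5. How often, under reading B.** Assume each participant has the same, independent chance q of loss in each three-month period. Then c is binomial(16, q), GROUP2 PABC losses are binomial(16 - c, q), GROUP1 PABC losses p1 are binomial(16, q), and w is binomial(16 - p1, q). Summing the exact probabilities of all patterns with seven or more lost and observed PABC retention of at least 85% gives:

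| Loss per period q | Loss over the study, 1 - (1 - q)^2 | Fails count although 85% met |
|---|---|---|
| 5% | 9.75% | 2.3% |
| 7.8% | 15% | about 13% |
| 10% | 19% | 24.9% |
| 15% | 27.75% | 36.9% |

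**The case against.** The strongest reply is that D.9 never says the count covers all 32 over the whole study. Hypothesis 1.1 supplies the window, so a PABC-only count is a fair reading, and the link to 32 - 26 is inferred from the sample-size section. That stands: reading B is not established by the text. It does not rescue the rule, because under reading A the count is too lenient for an 85% target.

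A reader might infer that the n = 32 statement contradicts the attrition allowance. The documents do not support this. The statement describes the design, in which both groups receive PABC and all 32 can contribute. A planned number alongside a separate attrition allowance is ordinary.

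A reader might also take the chance of losing more than 6 of 32 (83% at 15% loss per period, 41% at 10%) as the chance of wrongly failing a successful intervention. It is not. Those figures include trials in which observed PABC retention also missed 85%, where failing is correct. The joint event has probability 36.9% and 24.9%.

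The higher loss rates also exceed what the plan expects. D.2 anticipates less than 15% attrition, and section C.3 reports 1 of 23 lost so far in the team's ongoing trial in dysvascular amputation. Nothing in the documents shows that wash-out losses would equal those in the other periods. This too stands, so the 5% and 7.8% rows are closer to the plan's own expectation.

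Finally, the count is not the only criterion, because D.9 also tests attrition against 15%. The probabilities here concern the count alone. The test has the same undefined denominator and window, so it does not settle the question.

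**Conclusion.** The point holds as a mismatch between the hypothesis and its decision rule. That the count is not 15% of 32 is plain arithmetic and needs no assumption. The direction of the resulting error depends on a definition the plan does not give. Counting PABC losses only, five or six losses among 32 starters pass while missing the target. Counting all losses, an intervention that met 85% can fail. The chance of that is small at low attrition (2.3% at 5% per period), about 13% if total attrition is 15%, and larger above that. These probabilities rest on 16 per group, on equal and independent loss in each period, and on everyone still enrolled starting PABC.

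The documents do not show that the sponsor intended whole-study counting, or that the rule is only too harsh. What they show is a threshold that fits the 85% PABC-period target under neither reading.

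**What to change.** In D.9, define H1.1 retention as the number completing the end-of-PABC visit (3M for GROUP1, 6M for GROUP2) divided by the number who started PABC. Apply the 15% attrition cut-off to that rate, and use the same numerator and denominator in the test against 15%. Delete the count of more than 6 participants. If a count is wanted for orientation, at most 4 losses are compatible with 85% for 27 to 32 starters. Report GROUP2 control-period losses and GROUP1 wash-out losses separately, so that overall study attrition remains visible.

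The cost is wording only, since both visits are already scheduled. The downside is a slightly smaller denominator for Aim 1 if GROUP2 participants leave before Month 4.

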Physical-Activity Behavior-Change (PABC) Intervention. The PABC intervention will occur during Months 1-3 for GROUP1 and Months 4-6 for GROUP2 (Fig.1). The intervention begins with a home visit in which the therapist delivers and outlines the PABC intervention and use of equipment (FitBit wearable sensor (FitBit Inc., Boston MA) and FitBit application on the tablet). The FitBit wearable sensor is designed specifically to provide user feedback through an

Table 2. PABC Intervention Overview	
Technique	General Content of Weekly Visit*
Education	1. Specific weekly educational message 2. Participant feedback on message 3. Therapist clarification as needed
Self Monitoring	1. Promote self-monitoring using FitBit 2. Self-monitoring goal creation
Tailored Feedback	1. Direct feedback from FitBit application
Barrier Identification	1. Participant input on barriers 2. Therapist assists identification 3. Falls & adverse events recorded
Promotion of Problem Solving	1. Ideas for addressing barriers 2. Participant and therapist provide input
Action Planning	1. Collaborative weekly action plan 2. Guideline: 3% ↑ in weekly steps 3. Goals based on individual needs
Encouragement	Therapist ends session by: 1. Reviewing the "take home" message 2. Reviewing action plan for next week 3. Acknowledging achievements

application on the home-based tablet. (FitBit Use Handout)

The first intervention week will be an accommodation period for the participant to interact with the equipment and establish baseline activity feedback. After the first week, an individualized participant action plan will be developed and the therapist will deliver the intervention following a semi-structured script (Tab.2). Weekly video-based interactions between participant and therapist (30 minutes) will occur during the 3-month intervention (12 visits) using the mobile-health tablets. The PABC intervention will require daily participant interaction with the tablet application. The tablet application is commercially available through FitBit and will provide feedback on number of steps taken and progress toward activity goals. Participants' activity will guide the goals for each week and barriers to reaching goals will be identified. The therapist will guide the participant in reasoning how to address any identified barriers to activity progression.

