Each week will include scripted education delivered by the therapist during the video interaction, on a relevant intervention topic (e.g., fall prevention, monitoring blood sugar and diet relative to increasing activity, etc.) (10 minutes). The initial education topic will be fall prevention, to minimize fall risk during the study period.

No-Exercise Attention Control Period. During Months 1-3, GROUP2 will weekly have weekly video interactions with a therapist using the mobile-health tablets, in a no-exercise control period. These meetings will provide health and safety education on non-exercise topics pertaining to older Veterans (e.g., fall prevention, diet, medication management, retirement issues, etc.). Physical activity recommendations will not be discussed. Each week will include scripted education on one topic (10 minutes) and a brief period of light upper and lower extremity range of motion tasks led by the therapist with the video interface and participants seated in a chair (20 minutes). As in the PABC intervention period, the initial education topic for the Control period will be fall prevention, to minimize fall risk during the study period. The rationale for the no-exercise control period is to determine the natural change in physical activity and disability without PABC intervention, while accounting for any potential benefit from contact with the physical therapist (i.e., attention control).

D.6. Outcomes

Outcomes will be measured during in-home visits (Baseline, 3M, and 6M), instead of remotely, to promote safety and reduce fall risk during the test session. Aim 1 outcomes will be 1) participant retention rate, 2) dose goal attainment, 3) acceptability (Intrinsic Motivation Inventory – Interest/Enjoyment Subscale¹⁰), and Adverse & Serious Adverse Events). Aim 2 outcomes, to assess effect size, will be average 10-day physical activity counts (ActiGraph monitors^{2, 11}) and self-report disability (Late-Life Function and Disability Index (LLFDI)^{12, 13}). In addition, Baseline descriptive measures include demographics, medications, cognition (Folstein Mini-Mental State Exam¹⁴), depression (Geriatric Depression Scale SF^{15, 16}), residual limb quality (Chakrabarty Scale¹⁷), sensory testing (Michigan Neuropathy Screen^{18, 19}), exercise readiness to change (Exercise Stages of Change^{20, 21}), prosthesis description, and comorbidities (Functional Comorbidity Assessment²²).

D.7. Data Management

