Determining feasibility of the PABC intervention will set the stage for implementing a larger efficacy study. The expected result is that Veterans with LLA can be enrolled and retained in the PABC intervention with adherence to a 3% weekly increase in physical activity dose. In addition, the effect size is expected to be ≥ 0.80 . While similar interventions have been feasible and successful for other chronic disease populations, this trial will be the first to target chronic physical inactivity behavior for Veterans living with dysvascular LLA.

D.11. Participant Safety

Anticipated adverse events include falls and medical complications due to DM and PAD. A Safety Officer ([name]) for the study will meet with the PI quarterly to review study progress and adverse events. [name] is the Outpatient Medical Director for Rehabilitation Services at the Denver VAMC. [name] is also an Associate Professor in the Department of Physical Medicine and Rehabilitation at the University of Colorado. Beyond his clinical expertise, [name] has experience in outcomes research related to patients with LLA and functional exercise interventions. Fall risk will be monitored using the TUG test and Falls Efficacy Scale-International (FES-I) at all test points (baseline, 3M, 6M). Also, occurrence of falls will be recorded at each of weekly visit in both the intervention and control periods. Fall occurrences and other adverse events will be reported on a quarterly basis to the Safety Officer. The incidence of falls, defined as “inadvertently coming to rest on the ground, floor or other lower level, excluding intentional change in position”,⁸⁴ will be of particular focus. All study-related falls (possibly, probably, or definitely) will be tracked. If the total number of falls reaches 4, the Safety Officer will review incidence by group. If the number of falls for the intervention group exceeds that of the control group by 3 (10% of enrollment) at any time, the study will be suspended until an evaluation of study relatedness for each incidence is performed by the Safety Officer.

D.12 Potential Pitfalls and Alternative Strategies

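### Non-fall adverse events have an explicit weekly prompt only in the PABC sessions, so the Months 1-3 comparison in H1.4 is at risk of unequal ascertainment

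*Combined protocol and SAP*

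**What the plan says.** Four places in the protocol bear on how AEs are found during Months 1-3.

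- **PABC session (D.5, Table 2).** Under Barrier Identification, the general content of the weekly visit includes "3. Falls & adverse events recorded". Table 2 is the semi-structured script that the therapist follows after a first accommodation week.
- **Control session (D.5, No-Exercise Attention Control Period).** "Each week will include scripted education on one topic (10 minutes) and a brief period of light upper and lower extremity range of motion" exercises, the latter seated and lasting 20 minutes. No AE item and no discussion of barriers is described.
- **Safety monitoring (D.11).** "occurrence of falls will be recorded at each of weekly visit in both the intervention and control periods". The section sends falls and other AEs to the Safety Officer each quarter, but does not say how the other AEs are collected.
- **Synopsis, evaluation schedule.** Falls, AEs and SAEs are recorded continuously, with no limit by group or period. No question, frequency or recorder is named.

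The analysis that uses these data is H1.4 in D.9. AE/SAE rates, in events per participant, "will be compared between groups for Months1-3 (PABC intervention for GROUP1, attention control for GROUP2"). Similar rates are expected, and the Safety Officer and research team make the assessment. No test, alpha or margin is given.

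**The concern.** A comparison of AE rates is fair only if events are looked for in the same way in both groups. Here the one explicit weekly prompt that covers non-fall events belongs to the experimental session. It also sits inside a conversation about what limited the participant's activity, a setting that could plausibly bring out physical complaints. The control call, as described, consists of education and seated movement.

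Non-fall events matter in this trial: D.11 anticipates medical complications of diabetes and peripheral artery disease alongside falls. The design is described as tester-blinded only, and the Table 2 item is handled in a session led by the treating therapist, who knows the group. With 16 participants per group, a handful of unreported events changes the rate. Non-fall events that were never elicited cannot be recovered at the analysis stage.

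At stake is one of the four feasibility conclusions in the Primary Aim. Under-capture in the control group could make PABC look less safe when true rates are equal, or hide a true excess of events in the control group.

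**Working it through.** The plan states no AE rate, margin or test for H1.4, so there is no figure of its own to reproduce. The check has two parts.

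**1. Provisions side by side, Months 1-3**

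| Provision | GROUP1 (PABC) | GROUP2 (control) |
|---|---|---|
| Weekly therapist video contact (D.5) | yes | yes |
| Falls recorded at each weekly visit (D.11) | yes | yes |
| Other AEs named in the session description (D.5) | yes, Table 2 | no |
| AEs/SAEs recorded continuously (synopsis) | yes, method not given | yes, method not given |

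The groups differ in one row only, and that row concerns non-fall AEs.

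**2. What unequal capture would do (illustration)**

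Inputs: 16 in GROUP1 (section D) and 32 − 16 = 16 in GROUP2. The following are assumptions, not document figures: the true rate λ of non-fall AEs per participant over three months, equal in both groups, and c, the fraction of non-fall AEs captured in control relative to PABC.

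Apparent non-fall rate ratio (PABC/control) = λ / (cλ) = 1/c:

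- c = 1: 1.00
- c = 0.8: 1/0.8 = 1.25
- c = 0.6: 1/0.6 = 1.67
- c = 0.5: 1/0.5 = 2.00

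For all AEs together, let f be the share of captured PABC events that are falls, with falls captured equally in both groups. The ratio becomes 1 / (f + (1 − f)c). With an assumed f = 0.5:

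- c = 0.8: 1/(0.5 + 0.40) = 1.11
- c = 0.6: 1/(0.5 + 0.30) = 1.25
- c = 0.5: 1/(0.5 + 0.25) = 1.33

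Expected captured non-fall counts at λ = 1 are 16 × 1 = 16 in GROUP1. In GROUP2 they are 16 × 0.8 = 12.8, 16 × 0.6 = 9.6 or 16 × 0.5 = 8.

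To show what such counts could lead to, suppose Poisson counts and a two-sided exact conditional binomial test at 0.05. The plan specifies no such test. The chance of a nominally significant difference when true rates are equal is:

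| λ | c = 1 | c = 0.8 | c = 0.6 | c = 0.5 |
|---|---|---|---|---|
| 0.25 | 1.8% | 2.1% | 3.4% | 4.6% |
| 1 | 3.2% | 6.1% | 18.1% | 29.5% |
| 2 | 3.8% | 10.9% | 38.4% | 59.4% |

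When events are rare the distortion would seldom reach nominal significance. When they are common it often could.

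**The case against.** The strongest reply is that this reads too much into a short paragraph. The control session is described in narrative form, with no counterpart to Table 2. That narrative also leaves out the weekly fall recording that D.11 requires in the control period. Its silence therefore does not prove that a task is absent, and staff may well ask both groups about all AEs. Table 2 is itself an overview of general content: it says that events are recorded, not how they are asked about. That barrier discussion draws out more complaints is inference. H1.4 is a descriptive judgement in a 32-person pilot, and a falls-only comparison would rest on data recorded weekly in both groups.

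Most of this stands, and it rules out several stronger readings. A reader might infer that non-fall AEs are not recorded in the control period at all; the synopsis rule on continuous recording contradicts that. A reader might infer that the comparison is shown to be biased; the documents show an unstated procedure, not a stated difference, and c could be 1. A reader might also apply a ratio such as 2.0 to all AEs; falls are recorded weekly in both groups, so it would apply to non-fall events only.

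What the reply does not remove is that staff who follow only what is written would be prompted weekly for non-fall AEs in one group and not in the other. Continuous recording without a method does not equalise this. A falls-only analysis would leave the diabetic and vascular complications that the plan anticipates uncompared.

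**Conclusion.** The concern holds as a risk of unequal ascertainment, limited to non-fall AEs in the Months 1-3 comparison. The likely direction is against PABC, because its session carries the extra prompt. The size is unknown: 1/c for non-fall events and less for all AEs, with c and the fall share not given in the documents. The values 1.25 and 2.0 for non-fall events, and 1.11 and 1.33 for all AEs with half of them falls, illustrate assumed c of 0.8 and 0.5. They are not estimates.

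Falls data, and the D.11 review and suspension rules that count falls, are not affected by this point. The matter is still more than missing detail, because a Primary Aim comparison depends on a procedure that the plan sets out for one group only, and the remedy fits into calls that already take place.

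**What to change.** State one elicitation procedure in D.5 and D.11. At every weekly video contact, in both the PABC and control periods, the therapist asks the same falls-and-AE question, in the same wording and on the same form. It is asked separately from, and before, any discussion of barriers. Amend Table 2 and the control description to match.

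Keep recording AEs and SAEs that come to light by other routes, and count all of them in H1.4. Restricting H1.4 to events found by the query would drop events that continuous recording is meant to catch. Record the source of each event, so that query-elicited events can also be compared between groups on their own.

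The cost is one or two minutes per control call and a shared form, with no extra visits or staff. Slightly more AEs will be recorded in the control period. If staff already ask both groups the same question, a sentence saying so, with the wording used, closes most of the gap.
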